1.5.4 Incidence and Severity of Rejection and Anti- Donor Reactivity

These endpoints will be assessed at 52 weeks post-transplant. Biopsy grading and antibody assessments will be performed at the CTOT-15 Core Laboratories.

- 1. The incidence and severity of acute cellular rejection defined by the Kidney Banff 2007 criteria and Pancreas Banff 2011 criteria within the first 52 weeks.
- 2. The severity of first and highest grade of acute cellular rejection in the renal and pancreas biopsies
- 3. The incidence of humoral rejection in the renal and pancreas biopsies.
- 4. The prevalence of *de novo* anti-donor antibodies and anti-HLA antibodies.
- 5. The type of treatment of rejection.

1.5.5 Safety Outcome Measures

The following safety outcome measures will be assessed:

- 1. The incidence of death, graft loss, or undetectable c-peptide.
- 2. The incidence of all adverse events (AEs) and serious adverse events (SAEs).
- 3. The incidence of selected AEs and SAEs including:
 - Infections requiring hospitalization or systemic therapy,
 - BK and CMV viremia (local center monitoring),
 - EBV Infection (local center monitoring),
 - Malignancy.

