enroll in the pregnancy registry. The patient should also be apprised of the potential hazard of mycophenolate products to the fetus. The risks and benefits of CellCept/Myfortic should be discussed with the patient. In certain situations, the patients and her healthcare practitioner may decide that the maternal benefits outweigh the risks to the fetus.

If following initiation of study treatment, it is subsequently discovered that a subject is pregnant or may have been pregnant at the time of investigational product exposure, including during at least 56 days after product administration, the investigational product will be permanently discontinued.

Protocol-required procedures for study discontinuation and follow-up must be performed on the subject unless contraindicated by pregnancy (e.g., x-ray studies). Other appropriate pregnancy follow-up procedures should be considered if indicated. In addition, the investigator must report on the appropriate follow-up information regarding the course of the pregnancy, including perinatal and neonatal outcome. Infants should be followed for a minimum of 8 weeks. This pregnancy surveillance procedure includes male subjects who fathered a child while receiving study medication; however, male subjects do not need to discontinue study medication.

Viral Monitoring

The local center will monitor all subjects for CMV and BKV infection by quantitative PCR in the blood. This monitoring will take place at days 28 and 84, and at weeks 28, 52 and 76. The local center investigators will make all treatment decisions.

For Cause Biopsies - Renal

The center will perform a biopsy per the discretion of the Investigator in cases of increase in serum creatinine, proteinuria, or other clinical symptoms.

The local center will send the Pathology Core Lab ([name], UCSF) the following:

- 5 original stained slides (1-Trichrome or unstained, 1-PAS, 3 H&E) for histology reading.
- The site will send 1 SV40 and 1- immunohistochemistry C4d stained slides, if collected as standard of care.
- The remaining portion of the FFPE block will be stored at the local center and sent to the Core Pathology when requested for additional immunohistochemistry studies.

The local center will send the Molecular Core Lab ([name], University of Alabama) the following:

• 1 core in RNALater for gene expression, mRNA profiling studies.

Standard of Care or For Cause Biopsies- Pancreas

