13.2 Endpoint Assessments

13.2.1 Primary Clinical Endpoint

The primary endpoint will be the week-52 eGFR. Mean eGFR of the belatacept group will be compared to the mean eGFR of the tacrolimus reference group within a mixed models repeated measures (MMRM) framework , wherein repeated measures of eGFR at weeks 4, 12, 28, 36 and 52 will be modeled as a linear function of time (and perhaps other baseline covariates) in the 2 treatment groups. At week-52, a contrast will be made between the eGFR mean of the belatacept group and the eGFR mean of the tacrolimus group. ANCOVA assumptions will be evaluated graphically via standard residual analyses. If the assumptions fail, a suitable transformation (e.g., natural logarithms) will be found and the data will be reanalyzed on the transformed scale. Results will be reported with p-values associated with the F-test for each contrast and the corresponding mean treatment differences with two-sided 95% confidence intervals. All tests of significance will be two-tailed at the 0.05 level.

Estimating the contrasts within the repeated measures framework will provide treatment comparisons that are robust to subject dropout bias as long as the dropout pattern is missing at random²⁷. Data are missing at random whenever the "missingness" mechanism is a function of observable relationships among the nonmissing responses and covariates. Using the methods of Ma et al.²⁸, we will evaluate the MAR assumption in the data prior to implementing the MMRM analysis. If the MAR assumption fails, we will consider more robust alternatives (e.g., pattern mixture modeling)²⁹.

A number of studies have shown RMANCOVA to be superior to analyses of completers or of data with LOCF imputations³⁰. Nonetheless, we will conduct 2 related sensitivity analyses: (1) replace the missing week-52 values with the corresponding nonmissing week 36 values of each subject, dropping anyone who is missing both week-36 and week-52 and perform the ANCOVA as currently specified; (2) include only the completers in the ANCOVA analysis (i.e., exclude all dropouts). The sensitivity analyses will be included as additional secondary analyses.

13.2.2 Secondary Clinical Endpoints

The secondary endpoints are defined in Protocol section 1.5.

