Appendix 4. Reduced Follow-Up Schedule of Events (Recipient)

		D	AYS		S	
		28	84	24	36	52
	VISIT NUMBERS	4	6	9	12	16
	VISIT WINDOWS (+/- DAYS)	3	3	3	5	5
ASSESSMENTS	DETAILS					
	GENERAL ASSESSMENTS					
Physical Exam	Blood Pressure, Pulse, Temperature, Respiration, Weight	X	X	X	X	X
Immunosuppressive Medications	Drug Name, Dose, Start and End Date	\rightarrow	\rightarrow	\rightarrow	\rightarrow	\rightarrow
Assessments of Events	AE/SAE, Infections, Rejections, Hospitalizations, Graft Loss, Malignancies, New Onset Diabetes, Death	\rightarrow	\rightarrow	\rightarrow	\rightarrow	\rightarrow
Neurological Assessments for PML	History, mini mental, cranial nerve, motor, cerebellar exam	X	X	X	Х	Х
	LOCAL CLINICAL LAB ASSESSMEN	TS				
Hematology Panel	CBC, differential, Platelet	Х	Х	Х	Х	X
Chemistry Panel	Serum Creatinine	Х	Х	Х	Х	Х
Urinalysis	Protein, Glucose, Hematuria, WBC	Х	Х	Х	Х	Х
Viral Monitoring	BKV and CMV by PCR in blood	Х	Х	Х		
Viral Monitoring	CMV by PCR in blood					Х

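### The reduced follow-up schedule (Appendix 4) omits the week-52 BKV PCR that section 10.3 sets for all subjects, so BK viremia is ascertained differently on and off study therapy

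*Combined protocol and SAP*

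**What the plan says.** Section 10.3 (Viral Monitoring) states: "The local center will monitor all subjects for CMV and BKV infection by quantitative PCR in the blood". It then gives the times: "This monitoring will take place at days 28 and 84, and at weeks 28, 52 and 76". Appendix 2, the full first-year schedule, agrees and has local BKV and CMV PCR at days 28 and 84 and weeks 28 and 52.

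Section 8.7 sends subjects who stop study treatment before week 52 to Appendix 4. That schedule has two viral rows. The first, "BKV and CMV by PCR in blood", is marked at day 28, day 84 and week 24. The second, "CMV by PCR in blood", is marked at week 52 only. No reason is given for leaving BKV out of the second row.

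Section 1.5.5 lists BK viremia, found by local monitoring, among the selected safety events. Table 9 tests the incidence of specific infections between arms, one analysis per disease. The Study Definitions keep reduced follow-up subjects in the study for safety and applicable endpoint assessments.

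On renal function, section 13.2.1 says "The primary endpoint will be the week-52 eGFR" and that "repeated measures of eGFR at weeks 4, 12, 28, 36 and 52 will be modeled as a linear function of time". In Appendix 4 the row "Serum Creatinine" is marked at days 28 and 84 and weeks 24, 36 and 52. It has no week-28 column.

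**The concern.** A safety outcome compared between randomised arms should be looked for in the same way in everyone. If the sites follow Appendix 4 as written, a subject on therapy has a BKV PCR at week 52 and a subject off therapy does not. Viremia present at week 52 but not otherwise tested for would then be counted in the first group and missed in the second. The body text and the appendix also give the sites two different instructions, so practice may vary by centre.

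The creatinine mismatch raises a smaller question. The scheduled week-24 value exists only for subjects on reduced follow-up, and the plan does not say how the primary model should treat it.

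**Working it through.** **1. BKV PCR by local laboratory, schedules side by side, through week 52**

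| Source | Day 28 | Day 84 | Week 24 | Week 28 | Week 52 |
|---|---|---|---|---|---|
| Section 10.3, all subjects | yes | yes | – | yes | yes |
| Appendix 2 | yes | yes | – | yes | yes |
| Appendix 4 | yes | yes | yes | – | no (CMV only) |

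That is four scheduled tests against three, and the missing one is at the endpoint visit. Appendix 2 also has core-laboratory BKV PCR, including at week 52. Appendix 4 has no core-laboratory rows, so there is no stored sample to fill the gap.

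**2. Length of the untested period**

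- Stops before week 24: last scheduled BKV test at week 24, then 52 − 24 = 28 weeks with none.
- Stops after the week-24 visit and before the week-28 visit: Appendix 2 has no BKV test at week 24 and Appendix 4 has none later, so the last is day 84 (week 12), and the gap is 52 − 12 = 40 weeks.
- Stops after the week-28 visit: last test at week 28, then 52 − 28 = 24 weeks.

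**3. How many subjects**

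The documents give no discontinuation rate for this trial. With an assumed fraction d of the 60 subjects on Appendix 4 by week 52, the number without a scheduled week-52 BKV PCR is 60 × d. For d = 0.10 this is 6, and for d = 0.20 it is 12.

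**4. Effect on the comparison**

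Let v be the chance that an off-therapy subject has viremia that only the week-52 PCR would have found. Observed incidence in an arm is then too low by d × v. If v is the same in both arms, the difference between arms shifts by v × (d1 − d2), where d1 and d2 are the fractions on Appendix 4. Equal fractions cancel on the difference scale. They need not cancel on the risk-ratio scale that the plan uses. The documents give neither v nor d1 and d2, so the shift cannot be sized or signed.

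**5. Creatinine at week 24 instead of week 28**

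The visit windows do not overlap: week 24 ± 3 days is days 165–171 (168 ± 3), and week 28 ± 5 days is days 191–201 (196 ± 5).

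Inputs are 30 per arm and SD 20, from section 13.3. As a check on these, Table 11 reproduces. For SD 20, two-sided 0.05 and 80% power, (1.960 + 0.842) × 20 × √(2/30) = 14.47, or 14.71 with the t distribution, against 15.0 stated.

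The standard error of the week-52 contrast was computed by generalised least squares. Each subject contributes information XᵀV⁻¹X, with V = 20² × R. I is the sum over the 30 subjects in an arm, and SE = √(2 cᵀI⁻¹c) with c = (1, 52) for a line in time. Two inputs are assumed: within-subject correlation 0.5 to 0.9 (constant, or decaying per 12 weeks), and up to 50% of each arm on Appendix 4.

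| Case | SE, linear time |
|---|---|
| All at weeks 4, 12, 28, 36, 52 | 4.69 to 5.16 |
| 50% at week 24 instead of 28, used at actual time | 4.71 to 5.16 |
| 50% with the mid-year value discarded | 4.73 to 5.16 |

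The largest increases are 4.709 / 4.689 = 1.004 (0.4%) and 4.734 / 4.689 = 1.010 (1.0%). With a separate mean at each visit the SE is 20 × √(2/30) = 5.164 with or without the mid-year value, because week 52 is observed. For comparison, losing week 52 itself in 30% of subjects would give 4.94 to 5.48 (linear) or 5.30 to 6.03 (separate means). Appendix 4 does not cause that loss.

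**The case against.** The best defence is that section 10.3 describes the full schedule. Its list runs to week 76, which reduced follow-up subjects never reach, since section 8.7 follows them to week 52, and the same section refers to Appendix 4 separately. That may explain how the conflict arose. It does not remove it, because the sentence covers all subjects and nothing explains the omission.

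A second defence is that Appendix 4 still records infections throughout, and the Study Definitions define BKV infection as viremia that led the centre to alter immunosuppression. Such an infection remains reportable. This narrows the loss, but viremia has to be found by a test before it can prompt a change.

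Third, the group is limited. Section 8.5 keeps subjects with rejection during or after tacrolimus withdrawal on Appendices 2 and 3. Later discontinuers use Appendix 3. The amendment leaves active subjects on whichever schedule they already follow. This stands.

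A reader might also draw four stronger conclusions that the documents do not support:

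- That primary data are lost. Week-52 creatinine is kept, and so is week 36, which the first sensitivity analysis uses.
- That the week-24 creatinine goes unused. Secondary endpoint 5 in section 1.5.1 uses creatinine from all scheduled visits, and a model linear in time can take the value at its actual date.
- That the missing-at-random assumption is weakened. Appendix 4 keeps observing off-therapy subjects through week 52, which helps that assumption.
- That one arm is under-ascertained because it discontinues more. No by-arm rate for this trial is given. In the earlier kidney study (Table 1A), discontinuation for adverse events was 17.6% and 21.1% on belatacept and 19.7% on cyclosporine. One trigger in section 8.7, missed belatacept infusions, can arise only in the investigational arm, but that does not establish a higher overall rate.

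**Conclusion.** The BKV point holds as a minor but real contradiction. Under Appendix 4 as written, subjects off study therapy have no scheduled BKV test after week 24 and no core-laboratory backup, so BK viremia is ascertained differently by therapy status. What is at risk is viremia at week 52 that no other test finds and that changes no treatment. The 6–12 subjects rest wholly on an assumed 10–20% discontinuation. Any bias between arms depends on by-arm discontinuation and viremia rates that the documents do not give.

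The creatinine mismatch is secondary. One supporting visit has no stated place in the primary model, and the effect on precision is 0% to 1.0% under the assumed correlations, even with half of each arm affected.

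**What to change.** Reconcile section 10.3 and Appendix 4 so that week-52 BK viremia is ascertained in the same way in all subjects, using the blood already drawn for the week-52 CMV PCR. If the omission is intended, state in the report that week-52 BK viremia was not systematically assessed off therapy, and limit the between-arm comparison accordingly, for example to the period in which both schedules test for BKV.

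Add one sentence to section 13.2.1 saying that creatinine taken at week 24 under Appendix 4 enters the primary model at its actual time.

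The cost is at most one extra PCR per affected subject at a visit where blood is already taken, plus a few lines of text. The current version is dated June 28, 2016 and the study completes on August 31, 2016, so a schedule change would reach few remaining visits. The analysis and reporting wording can still be fixed in full before database lock.
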